## Sharing of Results

1 \* Describe whether results (study results or individual subject results, such as results of investigational diagnostic tests, genetic tests, or incidental findings) will be shared with subjects or others (e.g., the subject's primary care physicians) and if so, describe how it will be shared:

Safety monitoring will report incidental findings to the patient's primary care provider. The individual subject results will not be shared with the subjects. Aggregated data will be reported through oral and written presentations.

*ID: VIEW4E02808CBD800  
Name: v2\_Sharing of Results*

## Psychological/Behavioral/Educational Methods & Procedures

You indicated on the "Type of Research" page that your study involves a psychological/behavioral/educational method or procedure such as a survey, questionnaire, interview, or focus group.

1 \* Select all behavioral methods and procedures which apply to this study:

- Surveys/questionnaires
- Key informant or semi-structured individual interviews
- Focus groups or semi-structured group discussions
- Audio or video recording/photographing
- Educational tests or normal educational practices (education instructional strategies, techniques, curricula, or classroom management methods)
- Individual or group behavioral observations
- Psychosocial or behavioral interventions
- Neuropsychological or psychophysiological testing
- Deception
- Other psychosocial or behavioral procedures

ID: VIEW4E09416F57800

Name: v2\_Psychological/Behavioral/Educational Methods and Procedures

## Surveys/Questionnaires

You indicated that this study involves surveys and/or questionnaires.

If you uploaded a separate research protocol document in the 'Research Protocol' page, cite the applicable section and page numbers from that document in the answer boxes below.

1 \* List all questionnaires/surveys to be used in the study, including both standardized and non-standardized assessments:

Pain (basic)  
Pain scale (DoD/VA-based) diary

Pain-related function, interference, purpose and self-efficacy:

PROMIS-29 Profile v2  
PROMIS SF v1.0 Self-Effic-General  
PROMIS SF v1.0 Self-Effic-ManagSymptoms  
PROMIS SF v1.0 Meaning-Purpose

Pain (detail)  
Body pain diagram  
FM diagnostic criteria survey  
FM Patient pain location report  
Widespread pain index

Function and quality of life  
EQ-5D-5L  
SF-6D  
katz-ADL: activities of daily living  
Lawton-IADL: independent activities of daily living  
Life Space Questionnaire - Maryland

Sleep  
Pittsburgh Sleep Quality Index  
Insomnia Severity Index  
Epworth Sleepiness Scale

Diet  
ASA 24 dietary recall

App specific instruments  
System Usability Scale (SUS))  
Change Assessment in Pain Self-management

2 \* Upload a copy of all questionnaires/surveys:

Name	Created	Modified Date
4f. SPIRE_Accelerometer Activity Log wrist.docx(0.01)	5/31/2022 4:02 PM	5/31/2022 4:02 PM
1a. DoD-VA Pain Scale.pdf(0.01)	2/25/2022 12:55 PM	2/25/2022 12:55 PM
1b. Daily Pain Diary Cover Page_1.31.22.docx(0.01)	2/25/2022 12:55 PM	2/25/2022 12:55 PM
1c. Daily Pain Diary Pages_1.31.22.docx(0.01)	2/25/2022 12:55 PM	2/25/2022 12:55 PM
2a. PROMIS-29_Profile_v2.1_2-7-2018.pdf(0.01)	2/25/2022 12:54 PM	2/25/2022 12:54 PM
2b. PROMIS SF v1.0 - Self Effic-General 4a 9-1-17.pdf(0.01)	2/25/2022 12:54 PM	2/25/2022 12:54 PM
2c. PROMIS SF v1.0 - Self-Effic-ManagSymptoms 4a_6-21-2017.pdf(0.01)	2/25/2022 12:54 PM	2/25/2022 12:54 PM
2d. PROMIS_SF_v1.0_-_Meaning-Purpose_4a_6-27-2017.pdf(0.01)	2/25/2022 12:54 PM	2/25/2022 12:54 PM
3a. Body Pain Diagram with SML scoring sheet 2022FEB.docx(0.01)	2/25/2022 12:54 PM	2/25/2022 12:54 PM
3b. FM Diagnostic Criteria Survey Questionnaire (2013)_0.pdf(0.01)	2/25/2022 12:54 PM	2/25/2022 12:54 PM
3c. FM Patient Pain Location Report.pdf(0.01)	2/25/2022 12:53 PM	2/25/2022 12:53 PM
3d. Widespread Pain Index PDF.pdf(0.01)	2/25/2022 12:53 PM	2/25/2022 12:53 PM
4a. EQ-5D-5L Paper Self-Complete v1.1.docx(0.01)	2/25/2022 12:52 PM	2/25/2022 12:52 PM
4b. SF-6D_SF12-RCH.pdf(0.01)	2/25/2022 12:52 PM	2/25/2022 12:52 PM
4c. katz-adl.pdf(0.01)	2/25/2022 12:52 PM	2/25/2022 12:52 PM
4d. lawton-iadl.pdf(0.01)	2/25/2022 12:52 PM	2/25/2022 12:52 PM
4e. Life Space Questionnaire with Citation_Modified-Maryland.pdf(0.01)	2/25/2022 12:51 PM	2/25/2022 12:51 PM
5a. PSQI.pdf(0.01)	2/25/2022 12:51 PM	2/25/2022 12:51 PM

Name	Created	Modified Date
 5b. Insomnia Severity Index (ISI).pdf(0.01)	2/25/2022 12:51 PM	2/25/2022 12:51 PM
 5c. Epworth Sleepiness Scale (ESS).pdf(0.01)	2/25/2022 12:51 PM	2/25/2022 12:51 PM
 6a. ASA24_About Pages.pdf(0.01)	2/25/2022 12:50 PM	2/25/2022 12:50 PM
 7b. Change Assessment in Pain Self-Management_2022FEB25.docx(0.01)	2/25/2022 12:50 PM	2/25/2022 12:50 PM
 7a. System usability scale for App 2021DEC13.docx(0.03)	8/16/2019 2:37 PM	2/25/2022 12:50 PM

3 \* What is the total length of time that each survey is expected to take?

5 minutes each for a total of 60 minutes for first and last round of survey. The pain diary questionnaire will be answered daily during the study.

4 \* Are any of the questions likely to cause discomfort in participants or cause harm if their confidentiality were breached? (i.e., Illegal activities)

Yes  No

5 \* Do any questions elicit information related to the potential for harm to self or others?

Yes  No

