**1 \* Describe the purpose, specific aims, or objectives of this research. State the hypothesis to be tested:**

The purpose of this study is to develop and pilot test a novel App, in tablet-based form, to engage Veterans and providers in developing personalized, pro-active C-MEPPS for chronic low back pain. Our vision is an appealing user interface that increases Veteran access to self-management strategies, reliable information, and improved rehabilitative outcomes. The goal is to reduce pain impact and increase functional outcomes. This SPIRE effort will build and pilot test a web-based application empowering Veterans to overcome cLBP with a coordinated multidimensional evidence-based plan for pain self-management created by the Veteran. The specific aims of this project are aligned with primary Veterans Health Administration (VHA) strategic objectives, especially Strategy 1.1.2: "VA focuses on outcomes to tailor Veteran choice"; and: "Online navigator tools/information empowers Veterans to make decisions". This project responds to Rehabilitation Research and Development priorities: "Non-pharmacological activity-based interventions for chronic pain impacting outcomes that may include pain reduction... and QoL." Our secondary goal is to provide primary care and specialty services at VHA a novel, innovative, technologically appropriate, informative, and readily available tool in the fight against debility and poor health in Veterans with chronic low back pain.

Specific Aims:

- 1) To develop and pilot test a web-based application for Veterans, including women Veterans and older Veterans, applying User-Centered Design principles, empowering Veterans to build and use coordinated multidimensional evidence-based plans for pain self-management, aligned with each Veteran's preferences, interests, and strengths.
- 2) To promote behavior change targeting rehabilitative outcomes by identifying potential barriers to App use, e.g., usability and use, and by acquiring pilot data regarding future direction rehabilitative outcomes, including objective measures, e.g., physical activity, sleep duration, and patient-reported outcomes such as pain interference and improved quality of life.

**2 \* Discuss the research design including but not limited to such issues as: probability of group assignment, potential for subject to be randomized to placebo group, use of control subjects, etc.:**

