  - o 1st followup phone call: The study subject will be contact by phone one week after the initial visit. Coaching on App use and troubleshoot of App and actigraph use will be provided. Brief pain and pain interference questionnaires will be administered.
  - o 1st follow up visit: the study subject will be coached regarding the tablet App and actigraph use, all questions will be answered. The study subject will complete brief questionnaires pertaining to pain, sleep, quality of life, prior App experience, and pain interference. The study subject will be fitted with an actigraph and instructed in the use of the device.
  - o 2nd followup phone call: The study subject will be contact by phone 3 weeks after the initial visit. Coaching on App use and troubleshoot of App and actigraph use will be provided. Brief pain and pain interference questionnaires will be administered.
  - o 3rd followup phone call: The study subject will be contact by phone 4 weeks after the initial visit. Coaching on App use and troubleshoot of App and actigraph use will be provided. Brief pain and pain interference questionnaires will be administered.
  - o 4th followup phone call: The study subject will be contact by phone 5 weeks after the initial visit. Coaching on App use and troubleshoot of App and actigraph use will be provided. Brief pain and pain interference questionnaires will be administered.
  - o Final visit, in person 6 weeks after the initial visit: the study subject will be debriefed regarding tablet App, all questions will be answered. The study subject will complete brief questionnaires pertaining to pain, sleep, quality of life, prior App experience, and pain interference. The study subject will be debriefed on use of the Actigraph device. The devices will be collected. A 6-minute walk test will be completed.
  - o Final follow up phone call: The subject will be briefly interviewed two weeks after final visit for final thoughts about the App use experience and any plans to change behaviors as a result of using the App for activity planning.
  - o Veterans from Empowering Veterans Program at the Baltimore-Loch Raven VA; (Site: Loch Raven VA)
  - o Female Veterans from the Women's health clinic; (Sites: Baltimore VAMHCS and Fort Meade VA)

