We will examine pilot data on usability, App use, and behavior change, and assess barriers to implementing changes planned by the Veteran through the App (failure mode analysis). The vision is that this will lead to future research on rehabilitation-oriented outcomes such as: functional measures, QoL, and pain.

Importantly, there will be no remote, network transmission of data using the tablet app during this study. Instead, completely de-identified information (i.e. data without any of the 18 HIPAA identifiers) will be entered and stored on the tablet for subsequent download when participants arrive at the VAMHCS facility for their planned in-person visits. Hence, there is no chance that VA sensitive information could be accidentally divulged by using the tablet in the manner detailed for this pilot study.

The data collected from participants with tablet APP is de-identified data. The tablet APP and tablet itself are VA approved so authorized connected to the VA network (WiFi and Wired).

2 \* Describe all procedures already being performed for diagnostic or treatment purposes (if not applicable to the study, enter "N/A"):

N/A

3 \* **Describe the duration of an individual participant's participation in the study:**  
The individual's participation in the study will not exceed 8 weeks.

4 \* **Describe the amount of time it will take to complete the entire study:**  
4 years

5 \* **Describe any additional participant requirements:**

Inclusion criteria include: Veterans receiving care at the VAMHCS, frequent or persistent low back pain (> 3 months), pain  $\geq 3$  on a 0-10 numeric rating scale, willing to participate in trial of non-pharmacological therapies for pain; ability to speak, read, and write as needed for study. Stable treatment.

ID: VIEW4E0280585B400  
Name: V2\_Study Procedures

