## Withdrawal of Participants

**If the questions below are not applicable to the research (i.e., chart review), enter "N/A".**

1 \* **Describe anticipated circumstances under which subjects will be withdrawn from the research without their agreement:**  
Participants will be withdrawn without their agreement under the following circumstances:  
the subject is too ill to continue in the study,  
there is evidence of incorrect use or unanticipated risk,  
the subject does not follow instructions from research staff,  
the PI or co-investigators decides that the study is not in the best interest of the participant.

These circumstances have been outlined in the VA mandated informed consent form.

2 \* **Describe procedures for orderly termination:**  
We will close the study after the last participant interaction occurs and all data has been collected.

3 \* **Describe procedures that will be followed when subjects withdraw from the research, including partial withdrawal from procedures with continued data collection:**  
If a participant decides to withdraw from the research, all data already collected will remain in the database, but no new data will be collected from the participant. This information is included in the VA mandated consent form.

ID: VIEW4E1B52531F800  
Name: v2\_Withdrawal of Participants

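### Does leaving the usability scale unscheduled, with withdrawal allowed for incorrect use, commit the pilot to a completers-only usability score?

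*Protocol*

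**What the plan says.** Surveys/Questionnaires, item 1, lists the study's instruments in blocks. The last block holds two App-specific forms, the System Usability Scale and the "Change Assessment in Pain Self-management". No instrument is tied to a phase or visit. Item 3 gives the time needed as "5 minutes each for a total of 60 minutes for first and last round of survey" and adds only that the pain diary is daily.

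In Study Procedures, Phase 3 (20 Veterans), the initial, first follow-up and final visits carry the same sentence: "The study subject will complete brief questionnaires pertaining to pain, sleep, quality of life, prior App experience, and pain interference". The weekly calls add pain and pain interference forms, with coaching and troubleshooting. After the final visit there is one more call: "The subject will be briefly interviewed two weeks after final visit for final thoughts about the App use experience".

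Aim 2 includes "identifying potential barriers to App use, e.g., usability and use", and the Phase 3 description ends with "We will examine pilot data on usability, App use, and behavior change", together with a failure mode analysis.

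Withdrawal of Participants, item 1, allows removal without agreement when "there is evidence of incorrect use or unanticipated risk", or when staff instructions are not followed. Item 3 says what happens when a participant chooses to leave: "all data already collected will remain in the database, but no new data will be collected from the participant".

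**The concern.** Read together, these sections suggest a chain. The only general timing statement names a first and a last round. If an App the participant has not yet used cannot be rated at the first visit, the first usable usability score comes at the final visit, six weeks later. Anyone removed earlier for incorrect use would then give no score and would also miss the closing call. Those are plausibly the people for whom the App worked worst, and a study of barriers needs them. The pilot's usability figure would look better than the App performed, and that figure is meant to inform outcome measures for the next proposal. The 60-minute figure adds to the doubt, because it does not match the length of the instrument list.

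**Working it through.** **1. The 60 minutes.** Inputs: 60 minutes and 5 minutes per form (item 3); block sizes from item 1.

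- Forms that fit: 60 / 5 = 12.
- Forms listed, apart from the diary: 4 (PROMIS) + 4 (pain detail) + 5 (function and quality of life) + 3 (sleep) + 1 (diet) + 2 (App) = 19, so 19 × 5 = 95 minutes. With the diary, 20 × 5 = 100.
- Non-diary list without diet: 18 × 5 = 90. Without the App forms: 17 × 5 = 85. Without either: 16 × 5 = 80. None gives 60.
- If 60 minutes covered both rounds together: 30 / 5 = 6 forms per round.
- Five combinations of whole blocks total 12. Three leave out the App forms (for example PROMIS + function + sleep = 4 + 5 + 3) and two include them (for example PROMIS + function + diet + App = 4 + 5 + 1 + 2).

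The figure therefore cannot show whether the two App forms belong to the first and last rounds. It is not an arithmetic error either. The list covers the whole study, questionnaires are also used in Phases 1 and 2, and nothing says that all 19 are given in one Phase 3 sitting.

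**2. When a usability score could be taken.**

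- *Initial visit.* The participant is introduced to the App and instructed in it, and the questionnaires are listed after that. Phases 1 and 2 themselves assess usability within one session, so a first-round score is possible.
- *First follow-up visit* (between the week 1 and week 3 calls). The questionnaires include prior App experience, which could cover usability.
- *Final visit.* This falls within item 3's last round.

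A score at the final visit only is one reading of three, and the text does not fix it.

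**3. What withdrawal stops.** The sentence ending data collection applies to a participant who decides to leave. For removal by staff, later collection is neither promised nor ruled out. Incorrect use is not defined, so it may or may not mean failure with the App.

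**4. Size if every adverse reading held.** Let w of 20 leave unscored, and suppose they would have scored d SD worse than completers. Both are assumptions. The completers' mean then exceeds the mean of all 20 by (w / 20) × d. The standard error of the completers' mean is 1 / √(20 − w) SD.

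| w | d | Bias (SD) | Standard error (SD) | Ratio |
|---|---|---|---|---|
| 2 | 0.5 | 0.05 | 1/√18 = 0.24 | 0.2 |
| 4 | 1.0 | 0.20 | 1/√16 = 0.25 | 0.8 |
| 6 | 1.5 | 0.45 | 1/√14 = 0.27 | 1.7 |

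The upper rows would matter to a reader of the score. But every loss is treated as linked to poor usability, although withdrawal for illness or by choice need not be. The protocol gives no withdrawal rate.

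**The case for a change.** The best case for a change is that the visit at which a form is given is protocol content. The application asks for procedures and when they are performed, no separate research protocol was uploaded, and no later analysis can recover a form that was never given. Aim 2 and the Phase 3 analysis both rely on usability and behaviour-change data, yet neither form is placed at a visit. A schedule table and one more five-minute form at the first follow-up visit would cost almost nothing.

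Much of this stands. The two forms are not assigned to a visit, the 12 forms behind the 60 minutes are not identified, and the record kept after removal by staff is not stated. Pointing this out to the study team would be fair.

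The claim of damage does not stand. The protocol assigns barrier identification to its qualitative component, which has other sources: troubleshooting on the weekly calls, recorded interview responses, the App debrief at the final visit, and use logs that enter the data when the tablet is returned. A participant removed early would miss the debrief and perhaps a score, but calls already made and a returned tablet would still contribute. An extra form at the first follow-up visit would still miss anyone who left before it. It is a reasonable preference, but its benefit depends on the same unfixed readings.

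**Conclusion.** No change to the plan follows. This is missing detail, not a stated rule that gives a wrong result. Staff must decide which forms go into each visit's packet before Phase 3 starts. The text leaves them free to give the usability scale at the initial, first follow-up or final visit, and to decide what to record after removal by staff.

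The bias needs several things at once: a score taken only at the final visit, incorrect use meaning failure with the App, no collection after removal by staff, and enough such removals with clearly worse scores. The protocol establishes none of them. Under the assumed ranges the shift is 0.05 to 0.45 SD, but no bias can be quantified from the document itself. The study states that it is not powered for significance and that its quantitative results are descriptive, so no error rate or power is affected. The ordinary reporting of how many of the 20 gave a score, and why the rest did not, would let a reader judge any shortfall.

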5.1 If Yes, what procedures are in place to assure safety?

ID: VIEW4E09460F5EC00  
Name: v2\_Surveys/Questionnaires

## Interviews

You indicated that this study involves key informant or semi-structured individual interviews.

1 \* Are any of the questions likely to cause discomfort in participants or cause harm if their confidentiality were breached? (i.e., Illegal activities)

Yes  No

2 \* Upload a copy of the interview script or guide that will be used to guide the interviews:

Name	Created	Modified Date
 Script for follow up phone interview.docx(0.01)	5/31/2022 4:09 PM	5/31/2022 4:09 PM
 RGP App Phone Screen & Script rev.docx(0.01)	5/31/2022 4:07 PM	5/31/2022 4:07 PM

3 \* What is the individual duration of each interview and what is the entire duration of the interviews?  
25 minutes each for a total of 2.5 hours

4 \* How will the interview responses be recorded and by whom?  
Research assistant will record interview responses, with telephonic audio recording

5 \* Do any questions elicit information related to the potential for harm to self or others?  
 Yes  No

5.1 If Yes, what procedures are in place to assure safety?

If there is a concerning answer to the question: "Are there any problems you're having that we need to be aware of?", this will be reviewed by the safety team and the participants PCP will be alerted to relevant concerns.

## Focus Groups

You indicated that this study involves focus groups or semi-structured group discussions.

1 \* Are any of the questions likely to cause discomfort in participants or cause harm if their confidentiality were breached? (i.e., Illegal activities)

Yes  No

2 \* Upload a copy of the interview script or guide that will be used to guide the interviews:

Name	Created	Modified Date
 Script for focus groups(0.02)	8/9/2019 2:38 PM	8/14/2019 3:28 PM

3 \* How much time are the groups expected to require?  
90 minutes

4 \* How will the data be recorded?  
Notes and audio recording

5 \* Do any questions elicit information related to the potential for harm to self or others?  
 Yes  No

5.1 If Yes, what procedures are in place to assure safety?

ID: V1EW4E094A8F91800  
Name: v2\_Focus Groups

## Audio or Video Recording/Photographs

You indicated that this study involves audio or video recording/photographing.

1

\* Indicate the type of recording (check all that apply):

- Video
- Audio**
- Still Photo
- Other

1.1

If Other, specify:

2

\* What is the purpose of the recording? (i.e., for therapeutic purposes, to establish treatment fidelity, or to establish reliability of assessments)

Ensure correct transcription of interview and focus group responses.

3

\* Could the recording be likely to cause discomfort in participants or cause harm if their confidentiality were breached?

- Yes
- No

4

\* How will individuals' identities be protected?

All recordings will be stored only on secure encrypted computers and destroyed at the end of the study period.

## Observation

You indicated that this study involves individual or group behavioral observations.

1 \* Please describe what is being observed.

Individual behavior will be assessed using examination and actigraphy recordings.

2 \* Are any of the observations likely to cause harm if confidentiality were breached? (i.e., Illegal activities)

Yes  No

3 \* How will individuals identities be protected?

All recordings will be stored only on secure encrypted computers and archived according to VA policy at the end of the study period.

4 \* How will observations be recorded?

Observations will be recorded in writing, electronic records, and audio recording.

